Official Title: The Effect of Dental Anxiety on the Success of Mandibular Anesthesia in Mandibular Molar Teeth with Symptomatic Irreversible Pulpitis: A Prospective Clinical Study

NCT Number: Not available

Date: 15/12/2024

Null Hypothesis (H₀): Dental anxiety does not affect the success of mandibular anesthesia in the treatment of symptomatic irreversible pulpitis in mandibular molar teeth.

Study arms: A prospective clinical trial with two parallel intervention arms. Participants will be divided into two groups based on their Modified Dental Anxiety Scale (MDAS) scores:

- Group 1 (Low Anxiety Group): MDAS score < 10
- Group 2 (Moderate to High Anxiety Group): MDAS score ≥ 11 (including those with dental phobia if MDAS > 19)

Sample Size Calculation: Using G*Power 3.1.9.7 software, based on an effect size of 0.8, $\alpha = 0.05$, and power = 0.80, the required sample size was determined as **26 patients per group**, totaling **52 participants**. The actual power achieved was 81%.

Materials and Methods:

Inclusion Criteria:

- Systemically healthy adults aged 18–65
- Mandibular molar teeth with symptomatic irreversible pulpitis requiring root canal treatment
- Radiographic evidence of closed apex and absence of periapical pathology
- Periodontal probing depth ≤ 3 mm
- Tooth mobility < 0.5 mm
- Pain score of 55–170 mm on the Heft-Parker Visual Analog Scale (HP-VAS) (i.e., moderate or severe pain)
-

• Exclusion Criteria:

- Systemic disease
- Teeth with open apex, periapical lesion, internal or external resorption
- Periodontal probing depth > 3 mm
- Tooth mobility > 0.5 mm
- HP-VAS score < 55 mm (no or mild pain)
- Pregnant patients or those with allergy to articaine

Procedure:

- All treatments and measurements will be conducted between 09:00 and 12:00 to minimize circadian and cortisol fluctuations.
- Patients will avoid food intake for at least 2 hours before treatment and abstain from caffeine, alcohol, tobacco, and intense exercise within 24 hours.
- Patients will rest in the dental chair for 5 minutes, then their demographic data will be recorded.
- MDAS will be administered to assess anxiety level.
- HP-VAS will be used to assess pre-treatment pain level.
- Pulse rate, SpO₂, and salivary cortisol levels will be recorded pre- and post-anesthesia.

Anesthesia Protocol:

- All procedures are performed by a single operator in a one-unit room.
- Topical anesthesia: 10% lidocaine spray (Locanest) applied for 60 seconds.
- IANB (Inferior Alveolar Nerve Block):
 - 1.8 ml of 4% articaine hydrochloride with 1:100,000 epinephrine (Ultracaine DS Forte) via 27G needle
- Buccal and lingual infiltration:
 - Additional 1.8 ml injection performed 5 minutes after IANB
- Block Failure Definition:
 - If deep lip numbness is not achieved within 15 minutes, the block is considered failed and the participant is withdrawn from the study.

Outcome Evaluation:

- During treatment, if the patient feels pain, they raise their hand, and the pain is marked on the HP-VAS.
- If required, supplemental anesthesia (PDL or intrapulpal) will be administered and recorded.
- Successful anesthesia: No or mild discomfort
- Failed anesthesia: Moderate or severe pain
- Cold test will be performed 15 minutes after IANB. If positive, additional anesthesia will be given.

Biological Sampling:

- Saliva samples will be collected 15 minutes before and after anesthesia.
- Samples will be stored at -80°C until analysis.
- Special sterile, single-use Sali-Tubes (SLV-4158, DRG, Germany) will be used.

Statistical Analysis:

All statistical analyses will be performed using SPSS Statistics 20 software (IBM Corp., Armonk, NY) at a 5% significance level. If the data are normally distributed, Student's t-test will be used to compare preoperative pain levels, salivary cortisol, SpO₂, and pulse rate across different anxiety levels. Chi-square test will be used to analyze the relationship between anxiety levels and the success rate of anesthesia.

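### The 26 per group and 81% power fit a t-test with d = 0.8; neither is shown to apply to the chi-square test of anesthesia success, the trial's only hypothesis

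*Combined protocol and SAP*

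**What the plan says.** The plan states one null hypothesis: "Dental anxiety does not affect the success of mandibular anesthesia in the treatment of symptomatic irreversible pulpitis in mandibular molar teeth". Under Outcome Evaluation, success is binary: no or mild discomfort counts as success, moderate or severe pain as failure. The Statistical Analysis section assigns this outcome to a chi-square test: "Chi-square test will be used to analyze the relationship between anxiety levels and the success rate of anesthesia".

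The other planned test is for continuous measures and applies if the data are normal: "Student's t-test will be used to compare preoperative pain levels, salivary cortisol, SpO₂, and pulse rate across different anxiety levels". No hypothesis is stated for any of these.

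The Sample Size Calculation paragraph says the number was obtained in G*Power, "based on an effect size of 0.8", with alpha 0.05 and power 0.80. It gives 26 per group, 52 in total, and adds "The actual power achieved was 81" (per cent). It does not name the outcome, the test, the metric of the 0.8 (d, w or h), the sidedness, or an expected success rate in either group.

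**The concern.** An effect size of 0.8 with no metric means different things for different tests. On a continuous outcome it is a difference of 0.8 standard deviations. On a yes/no outcome it has no meaning until it is turned into two success rates, and the plan gives none. If the calculation was made for a t-test, the 81% says nothing about the chi-square that tests the hypothesis.

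What is at stake is how a non-significant result is read. The null hypothesis is worded as no effect. A reader who carries the 81% over to the success comparison could take p > 0.05 as good evidence for it, when the trial may have had well under an even chance of detecting a difference of 20 points.

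**Working it through.** **Inputs from the plan.** Effect size 0.8, alpha 0.05, target power 0.80, 26 per group (52 in total), stated power 81%. Sidedness is not given; two-sided is assumed unless noted.

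**Step 1: reproduce the plan's figures.** For a two-sample t-test with n per group, the noncentrality is d√(n/2) on 2n − 2 degrees of freedom. With d = 0.8 and n = 26 it is 0.8 × √13 = 2.884 on 50 df, and power is 0.8075. At n = 25 power is 0.7915. So 26 is the smallest n that reaches 80%, and its power rounds to 81%. Both figures are reproduced.

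**Step 2: try the other readings of 0.8.**

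| Reading | Smallest n for 80% power | Power at the plan's size |
|---|---|---|
| Two-sided t-test, d = 0.8 | 26 per group | 80.7% |
| One-sided t-test, d = 0.8 | 21 per group (81.7%; n = 20 gives 79.9%) | 88.5% |
| Mann-Whitney, normal parent (efficiency 3/π), two-sided | 27 per group (80.4%) | 78.9% |
| Chi-square, w = 0.8, 1 df | 13 in total (λ = 13 × 0.64 = 8.32; 82.2%) | over 99.9% |
| Two proportions, arcsine h = 0.8 | 25 per group (80.7%) | 82.2% |

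For the last row, n = 2 × [(1.960 + 0.842)/0.8]² = 24.5, rounded up to 25. Power at 26 is Φ(0.8 × √13 − 1.960) = Φ(0.924) = 0.822. Only the two-sided t-test gives both 26 and 81%.

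**Step 3: what 26 per group gives for the test of the hypothesis.** All success rates here are assumptions. Power is exact: the binomial probabilities of all 27 × 27 possible tables are summed over those that reject at two-sided 0.05. The plan does not say which variant of the test will be used, so three are shown.

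| Success rates (%) | Uncorrected Pearson | Yates | Fisher |
|---|---|---|---|
| 60 vs 40 | 28.5% | 20.8% | 20.8% |
| 70 vs 50 | 32.1% | 23.3% | 23.3% |
| 80 vs 60 | 36.8% | 24.8% | 25.0% |
| 90 vs 70 | 46.9% | 29.1% | 32.2% |
| 95 vs 75 | 57.5% | 33.6% | 39.7% |
| 65 vs 35 | 56.8% | 46.9% | 46.9% |
| 70 vs 40 | 58.3% | 48.4% | 48.4% |
| 80 vs 50 | 65.4% | 53.7% | 53.7% |
| 90 vs 60 | 75.4% | 60.4% | 61.6% |
| 95 vs 65 | 84.3% | 68.7% | 72.9% |

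Only 95 vs 65 with the uncorrected test passes 81%.

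**Step 4: detectable difference.** The smallest difference with 80% power at 26 per group, in percentage points:

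| Higher rate | Pearson | Yates | Fisher |
|---|---|---|---|
| 50% | 34.8 | 38.2 | 38.2 |
| 70% | 38.8 | 42.0 | 42.0 |
| 90% | 32.2 | 37.4 | 37.4 |

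**Step 5: scale.** The pooled two-proportion formula is n = [1.960√(2p̄(1 − p̄)) + 0.842√(p₁(1 − p₁) + p₂(1 − p₂))]²/(p₁ − p₂)². For 80 vs 60 this is (1.960√0.42 + 0.842√0.40)²/0.04 = 81.2, so 82 per group. The same formula gives 93 for 70 vs 50 and 97 for 60 vs 40. With continuity correction the three become 91, 103 and 107.

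The 95% CI half-width for the difference at 26 per group is 1.96√[(p₁(1 − p₁) + p₂(1 − p₂))/26]. That is 21.1 points at 90 vs 70, 24.3 at 80 vs 60, 26.1 at 70 vs 50 and 27.2 at 50 vs 50.

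**Step 6: withdrawals.** Everything above assumes 26 per group are analysed. If lip numbness is not achieved, "the block is considered failed and the participant is withdrawn from the study", and the plan does not say whether such participants are replaced. If 23 per group remained (an assumption for illustration), t-test power would be 75.6% and Pearson power for 80 vs 60 would be 31.5%.

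**The case against.** The strongest reply has three parts.

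First, the plan's arithmetic is correct under a standard reading. What is missing is the name of the endpoint and test. That is true: this is an untied figure, not a miscalculation.

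Second, setting 81% against power for 20–30 point differences changes the effect size as well as the test. If the standardised effect is held at h = 0.8, exact Pearson power at 26 per group is about 81–83% (for example 83% at 80 vs 42, 81% at 70 vs 31, 83% at 90 vs 56). This stands, and it means 26 per group is adequate for an effect of that size with the uncorrected test. But h = 0.8 means a difference of about 29–39 points, which the plan neither states nor justifies, and Yates or Fisher give only about 66–75% there. Even if h was intended, the success rates would still have to be stated.

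Third, the plan sets no target difference, so 20–30 points is the reviewer's choice, and the plan never says that the 81% covers the success comparison. Both are true. Wider gaps do better: 80 vs 40 has 87% power and 90 vs 50 has 92% with Pearson. The detectable difference in Step 4 is therefore the fairest summary, since it needs no target. The 23-per-group case is likewise only illustrative.

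**Conclusion.** The concern holds. The plan's one power figure matches a two-sided t-test on a continuous outcome with d = 0.8, and it is not shown to apply to the chi-square test of the only hypothesis. Since the paragraph names no test, this origin is inferred, but the match is exact on both figures and no other reading checked achieves it.

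At 26 per group, and for a higher success rate of 50–90%, the success comparison has 80% power only for differences of about 32–39 points (uncorrected) or 37–42 points (Yates or Fisher). Under most of the assumed rates, power for 20–30 points is below 81%, and for 20 points it is well below. The exception is near the ceiling with the uncorrected test. These figures rest on assumed success rates, two-sided alpha of 0.05 and 26 analysed per group. No single corrected sample size exists, because the plan supplies no rates from which to compute one.

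**What to change.** Keep 52 patients and rewrite the Sample Size Calculation paragraph.

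1. Name the test and metric behind the 81%. If the inference above is right, for example: 26 per group gives 81% power for a standardised difference of 0.8 in a continuous outcome, two-sided t-test, alpha 0.05.
2. For anesthesia success, state the assumed rate in each group and the test variant (chi-square with or without continuity correction, or Fisher), and give the power or detectable difference that follows. State also whether withdrawn participants are replaced, so that the analysed number behind the figure is clear.
3. Report the difference in success rate with its 95% CI as the main result, and state that p > 0.05 will not be read as absence of effect.

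The cost is a reworded paragraph and one confidence interval in the results, with no extra patients. The drawback is that, under most plausible rates, the stated power for the success comparison will look less favourable than 81%.

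### The allergy exclusion names articaine only, so a patient with known lidocaine allergy is eligible although lidocaine spray is a routine step

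*Combined protocol and SAP*

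**What the plan says.** The Exclusion Criteria contain one allergy item: "Pregnant patients or those with allergy to articaine". The general health criteria do not mention allergy. The Inclusion Criteria ask for "Systemically healthy adults aged 18–65", and the Exclusion Criteria rule out systemic disease as a separate line.

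The anesthetic steps are these:

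- Topical (Anesthesia Protocol): "Topical anesthesia: 10% lidocaine spray (Locanest) applied for 60 seconds". No exemption or substitute is given.
- Block injection: "1.8 ml of 4% articaine hydrochloride with 1:100,000 epinephrine (Ultracaine DS Forte) via 27G needle". This is the only injected product that the plan names.
- Infiltration on the buccal and lingual sides, where the plan gives just a volume and a time: "Additional 1.8 ml injection performed 5 minutes after IANB". The agent is not named.
- Supplement during treatment (Outcome Evaluation): "If required, supplemental anesthesia (PDL or intrapulpal) will be administered and recorded". The agent is not named.
- After a positive cold test (Outcome Evaluation): "If positive, additional anesthesia will be given". The agent is not named.

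**The concern.** An allergy exclusion should match the drugs that the protocol gives. This plan names two anesthetic agents, articaine and lidocaine, and excludes allergy to only one. Followed to the letter, the rule admits a patient known to be allergic to lidocaine, and the next step sprays that patient with lidocaine.

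What is at stake is participant safety. There is also a smaller matter of conduct: an operator who sensibly withholds the spray departs from the written anesthesia protocol for that participant. The point covers only known or disclosed allergies, since no exclusion can act on an unknown one.

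**Working it through.** **Does any criterion cover lidocaine allergy?** Each anesthetic step is set against the eligibility list.

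| Step | Agent stated | Covered by the allergy exclusion? |
|---|---|---|
| Topical spray | 10% lidocaine | No |
| Nerve block | 4% articaine with epinephrine | Articaine yes; other components not named |
| Buccal and lingual infiltration | Not stated | Yes for articaine, if it is the same product |
| PDL or intrapulpal supplement | Not stated | Cannot be determined |
| Additional anesthesia after a positive cold test | Not stated | Cannot be determined |

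The first row is enough to establish the gap. The remaining criteria concern age, general health, tooth, periodontal and apical status, pain score and pregnancy. None refers to lidocaine, to a class of local anesthetics or to drug allergy in general.

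**Does the point touch the plan's own calculation?** Sample Size Calculation states 26 per group, 52 in total, with 81% power, "based on an effect size of 0.8, $\alpha = 0.05$, and power = 0.80". For a two-sided two-sample t-test with 1:1 allocation:

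- noncentrality = d × √(n/2) = 0.8 × √(26/2) = 2.88, on 2 × 26 − 2 = 50 degrees of freedom;
- power from the noncentral t distribution is 0.807 at n = 26 and 0.791 at n = 25.

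So 26 is the smallest group size that reaches 0.80, and the stated figure reproduces. Allergy status enters nowhere in it, and rewording the exclusion leaves it unchanged.

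**How many participants might be affected?** The documents give no frequency of known lidocaine allergy, so p below is an assumption shown over a range. With n = 52, the expected count is 52p and the chance of enrolling at least one such patient is 1 − (1 − p)^52.

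| Assumed p | Expected count, 52p | Chance of at least one |
|---|---|---|
| 0.01% | 52 × 0.0001 = 0.0052 | 1 − 0.9999^52 = 0.5% |
| 0.1% | 52 × 0.001 = 0.052 | 1 − 0.999^52 = 5.1% |
| 1% | 52 × 0.01 = 0.52 | 1 − 0.99^52 = 41% |

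The last column is the chance that such a patient is enrolled. It is not the chance of exposure or of a reaction, and the 41% depends wholly on the assumed upper end.

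**The case against.** The strongest case on the other side concerns weight. Nothing in the inference changes, and fewer than one affected participant is expected across the assumed range, which itself has no source in the documents. A single operator treats everyone, and a patient who discloses a lidocaine allergy would probably not be given the spray. The plan names only one injectable product, so the infiltration, and plausibly the supplements, may be that same articaine solution, whose main agent the exclusion already covers. The general health criteria might also be applied to keep out someone with a serious drug allergy, and screening could be described in consent material that was not available for this review.

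Much of this stands as a limit on importance. The unnamed supplemental agent is better treated as a request for clarification than as proof that a second uncovered drug is injected. Nothing in the documents makes allergy to epinephrine a particular worry, and the conclusion does not rest on it.

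The core reading survives. The plan lists articaine allergy apart from systemic disease, which would be unnecessary if the general health criteria already covered drug allergy. It describes no allergy-history check and no alternative topical agent. Relying on the operator's good sense does not correct a rule that, as written, admits the patient.

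**Conclusion.** The concern holds. The lidocaine spray alone establishes it: lidocaine is given without condition, and lidocaine allergy is not excluded. The gap is minor and confined to participant safety and eligibility wording. Its practical size cannot be taken from the documents; the estimate of less than one affected participant holds only if no more than 1% of enrolled patients have a known lidocaine allergy. It should rank below any point that alters the analysis or the classification of participants.

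**What to change.** Keep the pregnancy exclusion and reword the allergy part as: *known allergy to articaine, lidocaine, or any component of the anesthetic products used, including any agent used for supplemental anesthesia*. This covers the spray, the other constituents of the injected solution and whatever is used as a supplement. It would also help to name the agent for the infiltration, the PDL or intrapulpal supplement and the top-up after a positive cold test, so that the exclusion can be checked against a complete list.

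The cost is one phrase in one criterion. The design, the target of 52 and the analysis stay as they are. Under the assumed range, at most 0.52 patients in 52 would be newly excluded.

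### A three-hour window is the only clock-time control on salivary cortisol; recording sampling time and adjusting for it would sharpen a secondary comparison (minor)

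*Combined protocol and SAP*

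**What the plan says.** Four parts of the combined protocol and SAP bear on this point.

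- **Procedure** sets the clock-time control: "All treatments and measurements will be conducted between 09:00 and 12:00 to minimize circadian and cortisol fluctuations". It also restricts food, caffeine, alcohol, tobacco and exercise and adds a short rest in the chair. On the measurements it says: "Pulse rate, SpO₂, and salivary cortisol levels will be recorded pre- and post-anesthesia".
- **Biological Sampling** times saliva relative to the injection only: "Saliva samples will be collected 15 minutes before and after anesthesia". No section asks for the clock time of a sample.
- **Study arms** describes how the groups arise: "Participants will be divided into two groups based on their Modified Dental Anxiety Scale (MDAS) scores". No matching or balancing of appointment time is described.
- **Statistical Analysis** gives the comparison, conditional on normality: "Student's t-test will be used to compare preoperative pain levels, salivary cortisol, SpO₂, and pulse rate across different anxiety levels". No covariate is named, and the plan does not say whether the pre value, the post value or the change is compared.

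**The concern.** By choosing a morning window to limit cortisol fluctuation, the plan accepts that cortisol depends on the time of day. The window narrows that source of variation but leaves a spread of hours. The Anesthesia Protocol section specifies one operator in a one-unit room, so patients booked on the same morning are treated in sequence and sampled at different times.

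Two things follow. First, time of day adds variance to cortisol that an unadjusted t-test leaves in the error term. Second, because anxiety is observed and not assigned, nothing in the design makes appointment times alike in the two groups. If they differed systematically, the cortisol comparison would partly be a comparison of appointment times. As clock time is not recorded, such a difference could be neither seen nor corrected afterwards.

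What is at stake is the cortisol comparison alone.

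**Working it through.** **1. The plan's own figure.** Sample Size Calculation gives "26 patients per group", "based on an effect size of 0.8", with 5% alpha and 80% power. A two-sided two-sample t-test with d = 0.8 (noncentral t) has 79.1% power at 25 per group and 80.7% at 26. The stated 26 per group and 81% therefore reproduce. The endpoint behind the 0.8 is not named.

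**2. How far apart sampling times can be.** With one sample 15 minutes before anesthesia and one 15 minutes after, the pair spans at least 30 minutes. Inside 09:00–12:00, the pre-anesthesia sample falls between 09:00 and 11:30 at the latest, a spread of at most 2.5 hours. The post-anesthesia sample likewise falls between 09:30 and 12:00. Since treatment must also fit in the window, the true spread is probably smaller.

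**3. Assumed inputs.** The documents give no cortisol slope, SD or distribution of appointment times. I assume:
- a log-linear fall f of 30% to 50% over three hours;
- an overall log-scale SD of 0.4 to 0.6;
- sampling times spread evenly over the available range.

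**4. Variance due to time of day.** Log slope per hour = |ln(1 − f)| / 3, and SD due to time = slope × 2.5 / √12.

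| f | Slope per hour | SD due to time | Share if log SD 0.6 | Share if log SD 0.4 |
|---|---|---|---|---|
| 30% | 0.119 | 0.086 | 0.086² / 0.36 = 2.0% | 0.086² / 0.16 = 4.6% |
| 50% | 0.231 | 0.167 | 0.167² / 0.36 = 7.7% | 0.167² / 0.16 = 17.4% |

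The share is about 2% to 17%. Removing a share s shortens the confidence interval by 1 − √(1 − s), which is about 1% at s = 2.0% and 9% at s = 17.4%. If the spread is only 2 hours, the share is about 1% to 11%.

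**5. Chance imbalance is not bias.** With 26 per group and times spread evenly over 2.5 hours, the difference in mean time between groups has SD √(2.5²/12 × 2/26) = 0.20 h, a 95% range of about ±0.39 h. The t-test's error rate already covers chance differences of this kind, because the time effect sits in the residual variance.

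**6. What a systematic difference would do.** This step is purely conditional. Bias in SD units = slope (SD per hour) × difference in mean time (hours). Under no true anxiety effect, with 26 per group, the unadjusted t-test rejects as follows:

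| Systematic difference | 0.2 SD/h | 0.3 SD/h | 0.5 SD/h |
|---|---|---|---|
| None | 5.0% | 5.0% | 5.0% |
| 0.5 h | 6.4% | 8.3% | 14.3% |
| 1 h | 10.9% | 18.6% | 42.4% |

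The assumptions in step 3 correspond to slopes of 0.119/0.6 = 0.20 to 0.231/0.4 = 0.58 SD per hour, so the table covers most of that range. In 4,000 simulated trials per setting (times within a three-hour window, linear time effect), adding clock time as a covariate brought rejection to 5.0%–5.4% at every slope, for both the 0.5 h and the 1 h difference. A systematic difference of one hour would be about five times the chance SD in step 5, so it would need strong selection.

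**The case against.** **The window is a legitimate control, and the plan does not claim more for it.** This stands. The stated aim is to minimise fluctuation. A reader might infer that the plan treats time-of-day variation as eliminated; the text does not say so. The accurate statement is that the window is the only control aimed at clock time. The food, caffeine, alcohol, tobacco, exercise and rest provisions address other influences.

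**No link between anxiety and appointment time is shown.** This also stands. A reader might infer that anxious patients take later or earlier slots, so that the cortisol result is biased. Nothing in the documents supports that. MDAS is listed after the patient is seated and rested, so the documents give no route by which staff would book by group. Patient self-selection remains possible and, without recorded times, could not be checked.

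**A pre/post change would remove most of the time-of-day level.** Largely true: under a log-linear fall, a within-patient log change over a fixed interval does not depend on the starting time. But the plan does not say that change is analysed, and a comparison of pre-anesthesia levels would stay exposed.

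**Cortisol carries little weight in this trial.** Correct. A reader might take cortisol to be the objective check on the anxiety grouping, but no section gives it that role. The null hypothesis concerns anesthesia success, tested by chi-square.

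**The magnitude comes from outside the documents.** True of both the morning fall and the SD, so the size can only be given as a range. The upper end needs the steepest assumed fall together with the smallest assumed SD.

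**Conclusion.** The point holds as a minor one. The plan recognises that clock time matters for cortisol, limits it only by the window, and then compares non-randomised groups without using sampling time. The effect to expect is extra noise: about 2% to 17% of log-scale variance, given a 2.5-hour spread of sampling times, a 30% to 50% fall over three hours and a log SD of 0.4 to 0.6.

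Bias is a possibility, not a finding. It requires a systematic difference in appointment time between anxiety groups, which the documents neither show nor rule out. The false-positive rates in the second table should be read only as what would follow from such a difference.

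The test of anesthesia success, and hence the null hypothesis, is untouched.

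**What to change.** - Keep the 09:00–12:00 window.
- Record the clock time of each saliva sample, and report sampling times by anxiety group.
- In Statistical Analysis, replace the unadjusted t-test for cortisol with a linear model containing anxiety group and sampling time, on the log scale if the values are skewed.
- State which cortisol value is compared (pre or post) and, if the pre/post change is also compared, say so.

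Waking time could be asked for as well, but it is optional.

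The cost is one time field on the case report form and one degree of freedom in the model (52 − 2 = 50 becomes 49). No extra patients, visits or assays are needed. The time field should be in place before sampling begins, because a clock time not noted at collection may not be recoverable.

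### Anxiety groups are not randomised and the recorded demographics enter no analysis, so both the t-tests and the chi-square test of success can reflect age or sex mix

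*Combined protocol and SAP*

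**What the plan says.** Under Study arms, the groups are defined by a patient characteristic: "Participants will be divided into two groups based on their Modified Dental Anxiety Scale (MDAS) scores". No randomisation, matching, quota or stratification is described. Eligibility is broad: "Systemically healthy adults aged 18–65". There is no restriction by sex, and the exclusion of "Pregnant patients or those with allergy to articaine" implies that women are eligible.

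The Procedure section states: "Patients will rest in the dental chair for 5 minutes, then their demographic data will be recorded". It does not list the items.

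The Statistical Analysis section has two comparisons. For the continuous variables, on condition of normality, "Student's t-test will be used to compare preoperative pain levels, salivary cortisol, SpO₂, and pulse rate across different anxiety levels". For the outcome in the null hypothesis, "Chi-square test will be used to analyze the relationship between anxiety levels and the success rate of anesthesia". It names no covariate, regression model, stratified analysis or baseline comparison of demographics.

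The plan does control some outside influences on the measurements: "All treatments and measurements will be conducted between 09:00 and 12:00 to minimize circadian and cortisol fluctuations". It also sets fasting and abstinence rules and uses a single operator.

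**The concern.** A two-sample test on randomised groups can attribute a difference to the grouping factor, because other characteristics differ only by chance. Here the grouping factor is a trait that patients bring with them. If the low-anxiety and moderate-to-high-anxiety groups differ in age or sex, and if pulse, cortisol, pain or anesthetic success also varies with age or sex, part or all of a group difference may belong to demographics. A real association could equally be masked.

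The timing, fasting and single-operator rules standardise how measurements are taken. They do nothing to balance who is in each group. With no demographic table by group planned, a reader of the results could not judge whether the problem arose.

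The success comparison matters most, because it alone addresses the stated null hypothesis, and that hypothesis is worded in terms of anxiety affecting success.

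**Working it through.** **Inputs from the documents.** Effect size 0.8, α = 0.05, 26 per group, stated power 81% (Sample Size Calculation); unadjusted t-tests and chi-square test (Statistical Analysis).

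**Inputs assumed.** The documents give no sex mix, age distribution, or sex or age effect. Every such value below is an assumption, shown over a range.

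**1. The plan's own figure.** For a two-sided two-sample t-test with d = 0.8, the noncentrality is 0.8 × √(26/2) = 2.884, with 50 degrees of freedom and critical value 2.009. Power is 0.8075. The stated 26 per group and 81% are reproduced, by a calculation with no covariate term.

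**2. What the unadjusted difference contains.** Let b be the sex effect in within-sex SD units, and p₁ and p₂ the proportions of women in the two groups. With no anxiety effect, the expected group difference is b(p₂ − p₁), and its standard error is √{[2 + b²p₁(1 − p₁) + b²p₂(1 − p₂)]/26}. The ratio is the noncentrality of the t-test. Example: b = 0.5, 40% vs 70% women. The difference is 0.5 × 0.30 = 0.15, the standard error is √[(1.06 + 1.0525)/26] = 0.285, and the ratio is 0.526.

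**3. Chance that the t-test rejects when the sex-adjusted effect is zero.**

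| Sex effect (SD) | Women, low vs higher anxiety | Spurious difference (SD) | Noncentrality | Rejection, formula | Rejection, simulated |
|---|---|---|---|---|---|
| 0.3 | 50% vs 50% | 0 | 0 | 5.0% | 4.7% |
| 0.3 | 40% vs 60% | 0.06 | 0.214 | 5.5% | 5.4% |
| 0.3 | 30% vs 75% | 0.135 | 0.482 | 7.6% | 7.6% |
| 0.5 | 40% vs 60% | 0.10 | 0.350 | 6.4% | 6.4% |
| 0.5 | 40% vs 70% | 0.15 | 0.526 | 8.1% | 8.1% |
| 0.8 | 40% vs 60% | 0.16 | 0.537 | 8.2% | 8.4% |
| 0.8 | 40% vs 70% | 0.24 | 0.809 | 12.5% | 12.6% |
| 0.8 | 35% vs 75% | 0.32 | 1.084 | 18.6% | 18.6–19.0% |
| 0.8 | 30% vs 75% | 0.36 | 1.223 | 22.4% | 22.5% |

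A linear model with group and sex was simulated in four of these settings (0.5 SD with 40/60 and 40/70; 0.8 SD with 40/70 and 35/75). It rejected in 4.6% to 5.2% of trials.

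**4. Age.** The spurious difference is slope × age gap, both in SD units. It runs from 0.2 × 0.3 = 0.06 SD to 0.5 × 0.8 = 0.40 SD. It can add to the sex contribution or offset it.

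**5. Anesthetic success.** The same logic applies. If the success probability differs by Δ between the sexes and anxiety has no effect within sex, the group success rates differ by Δ(p₂ − p₁), for instance 0.30Δ with 40% vs 70% women.

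**6. Cost of adjusting for age and sex.** The noncentrality becomes 2.884 × √[(1 − R²g)/(1 − R²y)] on 48 degrees of freedom. R²y is the share of outcome variance that the covariates explain, and R²g the share of group membership.

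| R²y | R²g = 0 | R²g = 0.10 | R²g = 0.20 |
|---|---|---|---|
| 0 | 0.807 | 0.765 | 0.715 |
| 0.10 | 0.846 | 0.807 | 0.760 |
| 0.20 | 0.885 | 0.850 | 0.807 |

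**The case against.** The strongest reply is that the t-tests may be purely descriptive. The plan says only that the variables are compared across anxiety levels. If the question is whether anxious patients present with a higher pulse or more pain, the group means in the table really do differ, and rejecting equality is a correct answer. This stands: the percentages are error rates only for an age- or sex-adjusted effect. It does not rescue the success comparison, because the null hypothesis there is about anxiety having an effect.

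The second reply is that the size is all assumption. This also stands. A reader might infer that the planned t-tests carry a false-positive rate of 8% to 19%. The documents do not support that, since they give no sex mix or sex effect, and with little imbalance the rate is about 5%. The calculation also uses an untruncated normal outcome, whereas eligibility restricts preoperative HP-VAS to 55–170 mm, so the assumed sex effects may not carry over to pain.

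Third, a reader might infer that patients chose their group, or that adjustment would remove the bias at no cost. Neither holds. Patients are classified by a score. A model with age and sex addresses only those two variables, as far as they are modelled correctly, and it can lose power.

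Finally, the recording of age and sex is itself inferred from an unitemised reference to demographic data. The inference is reasonable, but the plan should make it explicit.

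**Conclusion.** The omission is real and worth correcting. Group membership is not randomised, the eligible population is mixed in age and sex, and no stated analysis uses the demographics. It reaches all five planned comparisons: pain, cortisol, SpO₂, pulse and anesthetic success.

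What is established is a risk of confounding, with no step in the plan that would reveal or reduce it. It is not established that the groups will differ in age or sex, or in which direction any distortion would run. Under the assumed sex effects, the consequence for the t-tests ranges from negligible to an error rate about four times nominal. Age is illustrated only as a spurious difference, and for success only the form of the distortion is given, not its size.

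**What to change.** 1. Name age and sex among the demographic data and tabulate them by anxiety group.
2. Beside each t-test, report a linear model with anxiety group, age and sex as terms, giving the adjusted mean difference with 95% CI. Keep the t-test as the unadjusted companion.
3. State which time point each comparison uses. For post-anesthesia pulse, SpO₂ and cortisol, add the patient's own pre-anesthesia value to the model. Label that result as a comparison of patients with the same starting level, since the starting level may itself be related to anxiety.
4. Beside the chi-square test, report a similarly adjusted logistic model for anesthetic success, with few covariates given 52 patients.
5. Fix these terms before the data are seen, and word conclusions as associations.

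The cost is a few lines of analysis wording and standard SPSS procedures, with no extra patients and probably no new data. The downside is a possible loss of precision when age and sex predict group but not outcome: power of 0.765 or 0.715 against 0.807 in the assumed unfavourable cases. Where they also predict outcome, power can be unchanged or higher, up to 0.885 in the settings shown.
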